3.4.2. Secondary outcomes

1. Correlation of the TOSL Lessons score with the PAOFI total score and the FACT-COG cognitive impairments subscore and total score
2. TOSL synthesizing summary score and TOSL memory for details score and the PAOFI higher level cognition score, PAOFI total score, and FACT-COG cognitive impairments subscore and total score at time 0
3. Correlation of the change in the TOSL Lessons score, synthesizing summary score, and memory score with the change in PAOFI total score, higher level cognition subscore, and FACT-COG cognitive impairment subscore and total score between session 1 and session 2, 3 months apart

3.5. Consent/Accent

Delegated study investigators who received consent training will approach eligible subjects for enrollment into the study. A copy of the signed consent form will be given to the patient, the original signed consent will be kept in a study binder. No study procedures will occur prior to obtaining informed consent.

3.6. Monitoring Subjects and Criteria for Withdrawal of Subjects from the Study.

Subjects may voluntarily stop at any time.

STATISTICAL CONSIDERATIONS/DATA ANALYSIS

4.1. Sample Size

Stage 1 (internal pilot):

After the 1st 10 people we will pause to consider the recruitment rate and feasibility.

10 people will also give 80% confidence that we will encounter in the pilot study at least one incident of some unanticipated problem that may arise with a probability of 15%. (Vichtbauer 2015)

We will estimate the recruitment rate as 10 divided by the number of months to recruit 10 people. For the full study to recruit 55 people in 18 months requires an average recruitment of 3 people per month. If we can recruit 10 people in 4 months (recruitment rate 2.5 people/month) that will be considered sufficient recruitment rate to proceed to the full study.

10 people will also allow an estimate of the dropout/noncompletion rate. If the observed dropout rate is 10%, a sample size of 10 people will provide an 80% two-sided confidence interval of 1 to 34%.

If the recruitment rate and dropout rate are sufficient for completing the main study in the allotted time, we will proceed to stage 2, which is the full study.

Stage 2

The TOSL lessons score is a numeric score from 0 to 10 that can then be split in quartiles. In cognitively normal seniors, the mean score is 3.35 with SD 1.29. The complex narrative memory subscale is a numeric score from 0 to 24. In cognitively normal seniors, the mean score is 16.35 with SD 3.88. (Anand 2010) The PAOFI has 33 questions, each measured on a 1-6 score. The higher cognitive learning subscale has 12 items, and the reported score is an average of these items. In healthy controls the mean was 1.32 with SD 0.40. In women with breast cancer with cognitive complaints, the mean score was 2.68 with standard deviation 0.9. The Higher Level Cognition subscore has a Spearman correlation of ~ 0.47-0.71 with other memory tests in women with breast cancer without cognitive complaints. We will use a Spearman correlation coefficient to compare the BHI subscales with the PAOFI subscales. If the correlation coefficient is 0.7, to have 95% confidence interval width of 0.33 or less, we need 50 people. 50 people will also give ~85% power to reject the null hypothesis of 0 correlation coefficient if the actual correlation is at least 0.4, at a one-sided significance level of 0.05. Assuming a 10 percent drop out, rate we will recruit 55 people.

Given the small number of evaluations, the coordinator will confirm there are no missing items on the FACT-COG and PAOFI.

FACT-COG will be scored using the version 3 scoring document (<https://www.facit.org/measures-scoring-downloads/fact-cog-scoring-downloads>) without scoring the 4 items indicated as “NOT CURRENTLY SCORED.”

Study participants’ VSLT score, TOSL score, the PAOFI score, FACT-COG score and their subscale score at baseline and follow-up will be summarized using descriptive statistics (N, min, max, mean, median, SD).

The following Spearman’s correlation coefficients will be calculated
between the TOSL Lessons score/VSLT score and the PAOFI higher level cognition subscale score
between the TOSL lessons score/VSLT score and the PAOFI total score, the FACT-COG cognitive impairment subscale score and total score
between TOSL synthesizing summary score, TOSL memory for details score and the PAOFI higher level cognition score, PAOFI total score, FACT-COG cognitive impairments subscale score and total score at baseline.
between the change (from baseline to follow-up assessments) in the VSLT score, TOSL Lessons score, synthesizing summary score, memory score and the change (from baseline to follow-up assessments) in PAOFI total score, higher level cognition subscale score, the FACT-COG cognitive impairment subscale score and total score.

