ACT I: Assessment of Cancer Related Brain Fog using the Test of Strategic Learning

Principal Investigator

[name], MS

Sub-Investigator(s)

**[name] B.A.
[name], MSW, LCSW, OSW-C**

**Patient Advocate
[name]**

Sponsor

**Inova Schar Cancer Institute
Inova Neurosciences**

April 20, 2022

Version 2

ABSTRACT

Title: ACT I: Assessment of Cancer Related Brain Fog using the Test of Strategic Learning

Short Title: ACT I.

Rationale: To determine the ability of the Test of Strategic Learning (TOSL) to detect cognitive impairment in people complaining of brain fog.

Objectives: We hypothesize that we can recruit 3 people per month and that the TOSL will have high correlation with PAOFI higher level cognition subscore. The primary objectives are: Time to recruit the first 10 patients and the correlation of TOSL Synthesizing Summary score with PAOFI score at time 0

Study Type: This is a prospective observational cohort

Study Design: 55 people will be recruited who are 18 years of age and older and diagnosed with stage I-III breast cancer within the last 5 years and who can operate a computer and read and understand English.

Study Methodology: Participants will complete the TOSL, the PAOFI, and the FACT-COG at enrollment and then 3 months later. Completion can be done in person or on a computer.

Statistical Methodology: After the 1st 10 people we will pause to consider the recruitment rate and feasibility. If we can recruit 10 people in 4 months (recruitment rate 2.5 people/month) that will be considered sufficient recruitment rate to proceed to the full study. If the recruitment rate and dropout rate are sufficient for completing the main study in the allotted time, we will proceed to stage 2, which is the full study. We will use a Spearman correlation coefficient to compare the TOSL subscales with the PAOFI subscales. 50 people will also give 80% power to reject the null hypothesis of 0 correlation if the actual correlation is at least 0.4, at a significance level of 0.05. Assuming 10 percent drop out, we will recruit 55 people.

INTRODUCTION

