2.3. Duration of Study

There will be two assessments, three months apart. The expected duration of recruitment is 18 months.

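### The Stage 1 bar of 10 people in 4 months (2.5/month) is below the 3.06/month that 55 people in 18 months of recruitment needs, so a pass does not show the recruitment timeline can be met (minor)

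*Combined protocol and SAP*

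**What the plan says.** The target rate is in section 4.1, Stage 1: "For the full study to recruit 55 people in 18 months requires an average recruitment of 3 people per month". The abstract (Objectives) has the same rate as a hypothesis: "We hypothesize that we can recruit 3 people per month". Section 2.3 fixes the calendar: "There will be two assessments, three months apart. The expected duration of recruitment is 18 months". The 18 months therefore cover recruitment only, and the last 3-month visit comes after them.

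The go rule follows directly in 4.1: "If we can recruit 10 people in 4 months (recruitment rate 2.5 people/month) that will be considered sufficient recruitment rate to proceed". Stage 2 is then made conditional in more general terms: "If the recruitment rate and dropout rate are sufficient for completing the main study in the allotted time". The abstract (Statistical Methodology) runs the two statements together: "sufficient recruitment rate to proceed to the full study. If the recruitment rate and dropout rate are sufficient for completing the main study".

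Two further statements in 4.1 bear on the gate. One is the pause: "After the 1st 10 people we will pause to consider the recruitment rate and feasibility". The other is the dropout estimate: "10 people will also allow an estimate of the dropout/noncompletion rate". Neither the length of the pause nor the time at which dropout is read is given.

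**The concern.** Time to recruit 10 people is the Stage 1 primary outcome (3.4.1), and feasibility of recruitment is Aim 1. The rule built on it should tell the team whether the full study fits its calendar. As written, 4.1 declares sufficient a rate that its own preceding sentence shows to be too slow for 18 months, and then requires a rate that is fast enough for the allotted time. At exactly 2.5/month the explicit bar says proceed and the general condition says do not. A team at the pause could defend either decision. If it proceeds on the bar, it does so under an 18-month figure that the accepted rate cannot meet.

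**Working it through.** **Inputs.** From 4.1: 55 people, 18 months, bar of 10 in 4 months, 50 people for the analysis, correlation 0.4 for power and 0.7 for the interval. From 2.3: the 18 months are recruitment. Poisson accrual at a constant rate, with no closure of enrolment, is an assumption made here; the documents give no accrual model.

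**1. The plan's own rates.**
- Needed: 55/18 = 3.06 per month, which the plan rounds to 3.
- Bar: 10/4 = 2.5 per month, as stated.
- Bar that would match the needed rate: 10/3.06 = 3.27 months.

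Both of the plan's rates are computed correctly. The mismatch is between them.

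**2. What the accepted rate delivers.**
- In 18 months: 2.5 × 18 = 45 people.
- Time to 55: 55/2.5 = 22 months.
- After a bare pass at month 4, the rate needed for the rest: (55 − 10)/(18 − 4) = 45/14 = 3.2 per month.

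**3. What a pass tells the team.** Let N(t) be Poisson with mean rate × t.

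| True rate | P(pass): N(4) ≥ 10 | P(N(18) ≥ 55, given a pass) |
|---|---|---|
| 2.5/month | 0.54 | 0.13 |
| 3.06/month | 0.78 | 0.59 |

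The last column sums over k ≥ 10 the probability of k recruits in 4 months times the probability of at least 55 − k in the next 14, and divides by P(pass). At 2.5/month this is 0.0695/0.542 = 0.13. At 3.06/month it is 0.458/0.776 = 0.59. Even an on-target study that passes is far from certain to reach 55 by month 18, so 59% is the proper comparator for 13%.

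**4. A tighter bar.** With a 3.27-month bar at a true 3.06/month, the expected count is 10, and P(N ≥ 10) = 0.54. Such a bar would stop an on-target study 1 − 0.54 = 46% of the time, against 1 − 0.78 = 22% for the 4-month bar.

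**5. Effect on the Stage 2 primary (baseline correlation).** Fisher z, variance f/(n − 3), power = Φ(atanh(0.4)/√(f/(n − 3)) − z). Here f runs from 1 + 0.4²/2 = 1.08 (Bonett–Wright) to 1, and z = 1.645 (one-sided) or 1.96 (two-sided). Both sides are shown because 4.1 states a one-sided 0.05 level and the abstract gives 0.05 without a side.

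| n | One-sided power | Two-sided power | 95% CI width at 0.7 |
|---|---|---|---|
| 50 | 87–90% | 80–83% | 0.33 |
| 45 | 84–86% | 75–78% | 0.35 |

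The width uses f = 1 + 0.7²/2 = 1.245. For n = 50 the limits are 0.499 and 0.829, width 0.330, which reproduces the plan's 0.33. For n = 45 they are 0.485 and 0.835, width 0.350. Both rows use one method, so the difference is about 3 points one-sided and 5 points two-sided.

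**The case against.** The strongest defence is that a target and a minimum for continuing are different things. Ten recruits give a rough rate: the exact 80% interval for 10 in 4 months is about 1.6 to 3.6 per month. A bar set somewhat below target protects a sound study from being stopped by chance, and step 4 shows how costly the matching bar would be. The clock also starts at the opening of recruitment (3.4.1), so a slow start counts against Stage 1. After a bare pass the rest of the study needs 3.2/month, only 5% above the 3.06 average (3.21/3.06 = 1.05). All of this stands, and it is why the bar should stay. But the documents never call the bar a tolerance. If it is one, a pass cannot also mean that the rate suffices for 18 months.

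It might be said that the allotted-time sentence is a second check that covers the gap. It gives no criterion of its own, and the text before it has already called 2.5/month sufficient.

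A reader might infer more, and the documents do not support it:
- *That the study was meant to finish in 18 months.* Section 2.3 gives 18 months for recruitment; follow-up comes on top.
- *That the pause costs some number of months.* The plan gives no length and does not say that enrolment closes. Any figure for delay would rest on an invented closure.
- *That dropout will be judged before most of the first 10 reach their second visit.* The plan does not say that the review takes place on the day the 10th person is recruited. An estimate of noncompletion naturally implies waiting for the second assessment. The timing is unstated, not wrong.

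**Conclusion.** The point holds and is minor. The explicit bar and the condition on the allotted time disagree, and the bar lacks the property that the plan attaches to it. At the accepted rate, recruitment takes 22 months rather than 18, or stops at 45 people rather than 55. These figures need only a steady 2.5/month. The 13% and 59% rest on constant-rate Poisson accrual with no closure of enrolment, and they would fall if enrolment closed for a time.

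It would be wrong to conclude that the bar is an arithmetic slip or that it must be raised, or that the Stage 2 primary is seriously underpowered. At 45 people the power loss is 3 to 5 points and the interval widens by 0.02. What is at stake is a go decision that can be read two ways and a recruitment period that is understated for a study that only just passes.

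**What to change.** Keep 10 people in 4 months, the pause and the sample size. In 4.1, say that the bar is a tolerance around the planned 3 per month. In 4.1, 2.3 and the abstract, replace the single 18-month expectation with wording such as: *Recruitment is expected to take 18 months at about 3 per month and up to about 22 months at the minimum accepted 2.5 per month, plus any time enrolment is closed during the pause.* Define the allotted time to match, so that the bar and the general condition give the same answer.

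If recruitment cannot run beyond 18 months, state instead that the bar corresponds to about 45 people enrolled, with a confidence interval width of about 0.35 at a correlation of 0.7.

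Do not move the bar to 3.27 months: it would stop an on-target study about 46% of the time.

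As a clarification only, state whether enrolment closes during the pause, and that the dropout estimate is read once the first 10 people have reached the 3-month visit.

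The cost is a few sentences and a longer stated recruitment period, which may need agreement from the funder and the site.

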1.2. Hypothesis

We hypothesize that the Brain Health Index domains of gist reasoning and complex narrative memory will negatively correlate with higher cognitive subscale of the PAOFI and changes in BHI will negatively correlate with changes in the higher cognitive subscale of the PAOFI

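### The documents do not settle which correlation carries the one-sided 0.05 test, so the stated 5% can become about 8.5–10% (two named primaries) or 20–26% (six hypothesis correlations) if any single success counts

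*Combined protocol and SAP*

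**What the plan says.** Four parts of the combined protocol and SAP bear on which correlation is tested.

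- **Section 4.1, Stage 2 sample size.** With 50 people, the power is put at about 85%. The test is described as one "to reject the null hypothesis of 0 correlation coefficient if the actual correlation is at least 0.4, at a one-sided significance level of 0.05". No pair of scores is attached to this test. The nearby sentence on the choice of statistic refers only to the subscales of the two instruments, in the plural. The abstract words its own power statement differently: "50 people will also give 80% power to reject the null hypothesis of 0 correlation if the actual correlation is at least 0.4". There the level is 0.05 with no sidedness given.
- **Section 3.4.1 and the abstract.** Both name the baseline correlation of Synthesizing Summary with the PAOFI score as the Stage 2 primary outcome. A few lines later, section 3.4.1 names Lessons against the PAOFI higher level cognition subscale as the Stage 2 primary end-point. Section 3.4.2 then lists Synthesizing Summary among the secondary outcomes.
- **Section 1.2.** The hypothesis is that "the Brain Health Index domains of gist reasoning and complex narrative memory will negatively correlate with higher cognitive subscale of the PAOFI", and that the changes correlate negatively as well.
- **Section 4.1, analysis list.** Spearman's "correlation coefficients will be calculated" for four groups of pairs. None is marked as primary, and there is no success rule or multiplicity statement. The first line joins the VSLT to Lessons, although the VSLT appears in neither 3.4.1 nor 3.4.2. The change correlations match the third item of 3.4.2 ("Correlation of the change in the TOSL Lessons score, synthesizing summary score, and memory score" with changes in the questionnaires), with the VSLT added.

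**The concern.** A 5% level describes a conclusion only if it is clear in advance which result decides that conclusion. Here two different correlations are both called primary, the test in 4.1 is tied to neither, and the hypothesis covers several more. An analyst could follow the document faithfully and still choose, after seeing the data, which coefficient to present as the planned test. A reader of the report could not then tell a planned confirmation from the better of two results or the best of six.

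What is at stake is the error rate behind the study's main claim, that the TOSL is an objective indicator of brain fog. The data themselves are not affected.

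**Working it through.** **Inputs.** From 4.1: n = 50 evaluable, true correlation 0.4, one-sided 0.05, stated power about 85%. From the abstract: 80% power at 0.05, sidedness not given. From 1.2, 3.4.1 and the list in 4.1: the pairs of scores. The documents do not give the correlations among the cognitive scores, among the questionnaires, or between visits, so these are assumed below.

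**1. Reproducing the stated power.** Power = Φ(atanh(r)/√(v/(n−3)) − z), with n − 3 = 47 and z = 1.645 for one-sided 0.05.

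- With 0.4 as the Spearman value, atanh(0.4) = 0.4236. Power is 89.6% (v = 1), 88.0% (v = 1.06) or 87.5% (v = 1 + r²/2 = 1.08, Bonett–Wright).
- With 0.4 as a Pearson correlation, the Spearman value is (6/π)·asin(0.2) = 0.385. Power is 85.4% (v = 1.06) or 85.0% (Bonett–Wright), which reproduces the stated figure.
- Simulated Spearman tests give 86.7% on the Pearson reading and 89.2% on the Spearman reading.
- With 0.4 as the Spearman value, a two-sided 0.05 test gives 80.5% (v = 1.06) or 79.8% (Bonett–Wright). The abstract's 80% therefore looks like a two-sided test.

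The 85% is the power of one test of one correlation.

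**2. Counting the correlations.** The four lines of the list give:

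- Lessons and VSLT against one questionnaire score: 2 × 1 = 2
- Lessons and VSLT against three more: 2 × 3 = 6
- Summary and Memory against four: 2 × 4 = 8
- changes in four measures against changes in four: 4 × 4 = 16

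The total is 2 + 6 + 8 + 16 = 32. The hypothesis in 1.2 covers two gist scores and memory, against higher level cognition only, at baseline and as change: 3 × 1 × 2 = 6.

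**3. Chance of at least one one-sided p < 0.05 when every true correlation is zero.** For k independent tests this is 1 − 0.95^k. The last column comes from simulated null data (n = 50, 10,000 runs, Monte Carlo standard error at most √(0.25/10,000) = 0.5 percentage points). The three values assume correlations among cognitive scores and among questionnaires of 0.3/0.5, 0.5/0.7 and 0.7/0.9, with test–retest correlation 0.7.

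| What may count as support | k | Independent | Correlated (assumed) |
|---|---|---|---|
| One pre-named correlation | 1 | 5% | 5% |
| Either named primary | 2 | 1 − 0.9025 = 9.75% | 9.5%, 8.7%, 8.5% |
| Any of the six in 1.2 | 6 | 1 − 0.7351 = 26.5% | 24.2%, 22.2%, 19.5% |
| Any listed coefficient at all | 32 | 80.6% | 63.5%, 51.3%, 36.6% |

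The second row pairs both Lessons and Summary with higher level cognition. If Summary is paired with another PAOFI score, the two tests share less and the result lies closer to 9.75%. The last row applies only if any coefficient may be cited as support, which the documents do not say.

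**4. Power under the possible remedies.** One named test at one-sided 0.05 keeps the power in step 1. Splitting 0.05 equally (Bonferroni) gives simulated power of 79–82% over two tests and 64–68% over six. The lower figure reads 0.4 as Pearson, the higher as Spearman.

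**The case against.** The strongest reply is that a hierarchy already exists. Section 3.4.1 names a single Stage 2 end-point, 3.4.2 ranks other correlations as secondary, and the list in 4.1 opens with Lessons against higher level cognition. The power sentence in 4.1 is worded in the singular, and the plural reference to subscales describes the statistic, not the test. The list says only that coefficients will be calculated; it promises no p-values. Section 4.1 justifies 50 people first by the width of a confidence interval, with power as an additional property. The hypothesis in 1.2 is joined by the word and; if all its parts must hold, the error rate cannot exceed 5%. Finally, unadjusted secondary correlations are common in a small observational cohort.

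Most of this stands, and it limits the point. A reader might infer that the 0.05 is tied to nothing, or that the study has a 37–81% chance of a false conclusion across 32 tests. The documents support neither reading: an end-point is named, and no rule lets any coefficient decide the study. The VSLT, PAOFI total and FACT-COG correlations are not part of the hypothesis.

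The reply does not remove the contradiction within 3.4.1, which the abstract repeats on the Summary side. Calling an outcome secondary does not say whether it will be tested or only estimated. Nothing states that all parts of the hypothesis must hold, and the planned power is for one correlation.

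**Conclusion.** The point holds in a limited form. The plan states a one-sided 0.05 test, but the documents do not settle which correlation carries it. With no true association, the 5% becomes about 8.5–10% if either named primary may count, and about 20–26% if any one of the six hypothesis correlations may count.

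Both ranges assume that a single success is taken as support. Their upper ends assume independent tests; the lower ends rest on assumed correlations among scores. If one named correlation decides, or if all parts must hold, there is no inflation. The defect is that the plan does not say which of these applies. The differing sidedness and power in the abstract and 4.1 belong to the same gap, because they too leave the primary test incompletely defined.

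**What to change.** Reconcile the abstract, 3.4.1 and 4.1 to one Stage 2 primary correlation, stating the two scores, the time point, the expected direction and the sidedness. Direction needs stating because 1.2 predicts a negative correlation, while 4.1 gives the alternative as a positive value. Then add to 4.1 that only this correlation is tested at 0.05, and that the other 31, including those with the VSLT, are reported as estimates with 95% confidence intervals and no confirmatory claim.

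If the sponsor wants claims on the remaining five hypothesis correlations, a Holm procedure opened only after the primary rejects would allow them at no cost to the primary. This is optional and a matter of preference in a study of this kind.

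The change costs a few sentences and no patients or data. Power for the primary stays at about 85–89% if the test remains one-sided; if two-sided is chosen, the abstract's 80% is the relevant figure. The small downside is that secondary correlations can no longer be called significant at an unadjusted 0.05.
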